4.3.2 WITHDRAWAL OF CONSENT

Patients are free to withdraw from the study at any time (treatment and assessments) without prejudice to further treatment.

Patients who withdraw consent for further participation in the study will not receive any further IP or further study observation, with the exception of follow-up for survival, which will continue until the end of the study unless the patient has expressly withdrawn their consent to survival follow-up. Note that the patient may be offered additional tests or tapering of treatment to withdraw safely.

A patient who withdraws consent will always be asked about the reason(s) for withdrawal and the presence of any AE. The Investigator will follow up AEs outside of the clinical study.

If a patient withdraws consent, they will be specifically asked if they are withdrawing consent to:

- all further participation in the study including any further follow up (e.g., survival contact telephone calls),
- withdrawal of consent to the use of their study generated data, and/or
- withdrawal to the use of any samples.

4.3.3 REPLACEMENT OF PATIENTS

Subjects who withdraw consent or otherwise become ineligible prior to receiving the first dose of investigational regimen will be replaced.

5. INVESTIGATIONAL PRODUCTS

5.1 DURVALUMAB

5.1.1 FORMULATION/PACKAGING/STORAGE

Durvalumab (MEDI4736) will be supplied by AstraZeneca as a 500-mg vial solution for infusion after dilution. The solution contains 50 mg/mL durvalumab (MEDI4736), 26 mM histidine/histidine-hydrochloride, 275 mM trehalose dihydrate, and 0.02% weight/volume (w/v) polysorbate 80; it has a pH of 6.0 and a density of 1.054 g/mL. The nominal fill volume is 10.0 mL. Investigational product vials are stored at 2°C to 8°C (36°F to 46°F) and must not be frozen. Drug product should be kept in original packaging until use to prevent prolonged light exposure.

5.1.2 PRODUCT PREPARATION AND DOSE ADMINISTRATION

Patients in the durvalumab monotherapy treatment group will receive Q3W dosing of 1120 mg durvalumab during the monotherapy cycle (Cycle 0).

In the Safety Lead-in Phase and during the combination treatments in Phase II, subjects will receive Q4W dosing of 1500 mg durvalumab (for patients >30kg in weight). Weight based dosing at 20 mg/kg will be utilized for any patient whose body weight drops below 30 kg while on the combination treatment.

The dose of durvalumab (MEDI4736) for administration must be handled and prepared by the Investigator's or site's designated IP manager using aseptic technique according to institutional guidelines. Total time from needle puncture of the durvalumab vial to the start of administration should not exceed:

- 24 hours at 2°C to 8°C (36°F to 46°F)
- 4 hours at room temperature

A dose of 1500 mg (for patients >30kg in weight) or 1120 mg will be administered using an intravenous (IV) bag containing 0.9% (w/v) saline or 5% (w/v) dextrose, with a final durvalumab (MEDI4736) concentration ranging from 1 to 15 mg/mL, and delivered through an IV administration set with a 0.2- or 0.22- μ m filter. Add 30.0 mL of durvalumab (MEDI4736) (i.e., 1500 mg of durvalumab [MEDI4736]) or 22.4 mL (i.e., 1120 mg of durvalumab [MEDI4736]) to the IV bag. The IV bag size should be selected such that the final concentration is within 1 to 15 mg/mL. Mix the bag by gently inverting to ensure homogeneity of the dose in the bag.

If patient weight falls to < 30 kg weight-based dosing at 20 mg/kg will be administered using an IV bag containing 0.9% (w/v) saline or 5% (w/v) dextrose, with a final durvalumab (MEDI4736) concentration ranging from 1 to 15 mg/mL, and delivered through an IV administration set with a 0.2- or 0.22- μ m filter.

Standard infusion time is 1 hour, however if there are interruptions during infusion, the total and allowed infusion time should not exceed 8 hours at room temperature. If preparation time or infusion time exceeds the time limits a new dose must be prepared from new vials. Durvalumab does not contain preservatives, and any unused portion must be discarded.

Do not co-administer other drugs through the same infusion line.

The IV line will be flushed with a volume of IV diluent equal to the priming volume of the infusion set used after the contents of the IV bag are fully administered or complete the infusion according to institutional policy to ensure the full dose is administered.

During combination treatment, durvalumab will be administered prior to AVB-S6-500. IV line flushing in between IP treatments will be performed per institutional policy.

5.1.3 MONITORING OF DOSE ADMINISTRATION

Patients will be monitored before, during and after the infusion with assessment of vital signs at the times specified in the Schedule of Assessment. Patients are monitored (pulse rate, blood pressure) every 30 minutes during the infusion period (including times where infusion rate is slowed or temporarily stopped).

In the event of a \leq Grade 2 infusion-related reaction, the infusion rate of study drug may be decreased by 50% or interrupted until resolution of the event (up to 4 hours) and re-initiated at 50% of the initial rate until completion of the infusion. For patients with a \leq Grade 2 infusion-related reaction, subsequent infusions may be administered at 50% of the initial rate. Acetaminophen and/or an antihistamine (e.g., diphenhydramine) or equivalent medications per institutional standard may be administered at the discretion of the investigator. If the infusion-related reaction is Grade 3 or higher in severity, study drug will be discontinued. However, a single occurrence of a Grade 3 reaction that resolves within 6 hours is permitted in the absence of prophylaxis. The standard infusion time is one hour, however if there are interruptions during infusion, the total allowed time from infusion start to completion of infusion should not exceed 8 hours at room temperature. For management of patients who experience an infusion reaction, please refer to the toxicity and management guidelines in **Section 6.3**.

As with any antibody, allergic reactions to dose administration are possible. Appropriate drugs and medical equipment to treat acute anaphylactic reactions must be immediately available, and study personnel must be trained to recognize and treat anaphylaxis. The study site must have immediate access to emergency resuscitation teams and equipment in addition to the ability to admit patients to an intensive care unit if necessary.

5.2 AVB-S6-500

The AVB-S6-500 is an Fc fusion protein of the extracellular portion of the AXL receptor that has been engineered to have higher affinity to GAS6 by the substitution of five amino acids in the AXL extracellular domain. The molecule consists of one of the genetically modified AXL receptors fused to each arm of a human Fc molecule (CH2 & CH3), thereby creating a dimer of the genetically modified AXL receptor.

5.2.1 FORMULATION/PACKAGING/STORAGE

AVB-S6-500 will be supplied by Aravive as a solution for injection with the composition of the formulated drug product (DP) shown in Table 1. AVB-S6-500 should be diluted in normal saline prior to infusion.

AVB-S6-500 DP vials are filled with 10 mL at 20 mg /mL (± 2 mg/mL) for a total of approximately 200 mg/vial into 20 mL Schott USP Type I glass vials with rubber stoppers and aluminum-plastic flip caps. Vials are filled on an automated aseptic filling line and stored at -20°C.

Vials of AVB-S6-500 drug product should be refrigerated in their box at 2-8°C until ready to use. Refer to Investigator's brochure and pharmacy manual for additional details.

Table 2. Formulation of AVB-S6-500 Drug Product

Components	Function	Amount
AVB-S6-500	Active	20 mg/ml ± 2 mg/mL
Polysorbate-80	Stabilizer	0.01%
Mono and disodium phosphate	Buffer to pH 7.0	10 mM
Sucrose	Stabilizer	9%

5.2.2 PRODUCT PREPARATION AND DOSE ADMINISTRATION

Parenteral drug products should be inspected visually for particulate matter and discoloration prior to administration, whenever solution and container permit. AVB-S6-500 should be diluted in normal saline to a total volume of 150 mL (to achieve the desired dose in mg/kg) and administered as an i.v. infusion over 60 minutes.

During combination treatment, durvalumab will be administered prior to AVB-S6-500. IV line flushing in between IP treatments will be performed per institutional policy.

5.2.3 PRE-MEDICATION FOR AVB-S6-500 DOSING

All patients must be premedicated with anti-H1 and anti-H2 prior to first administration of AVB-S6-500 (Cycle 0 in the AVB-S6-500 monotherapy group; Cycle 1 in the Safety Lead-In and durvalumab monotherapy groups) to reduce the risk and severity of infusion reaction.

Premedication (or components thereof) could be optionally omitted for future cycles, if no infusion reaction was observed during or after the first AVB-S6-500 infusion.

Steroids can be optionally included at the discretion of the treating physician, ideally administered the evening before and again the morning of dosing (for example, dexamethasone 12 mg PO the evening prior and 12 mg PO in the morning prior to dosing). If IV steroids are utilized on the morning of dosing, they should be administered at least 1 hour prior to dosing.

Most infusion reactions occur toward the end of the infusion, or after the infusion has been completed, and patients must be observed for at least 45 minutes after their first AVB-S6-500 infusion.

Any patient who experiences a reaction DURING the infusion and is deemed by the Investigator to be acceptable for same day rechallenge, should be premedicated prior to rechallenge, and the remainder of the infusion should be administered at one-half of the previous infusion rate.

Any patient who experiences a reaction AFTER the infusion and is deemed by the Investigator to be acceptable for rechallenge with the next dose, should be premedicated with an anti-H1, anti-H2, and steroid-containing regimen prior to rechallenge, and the duration of AVB-S6-500 at rechallenge should be 2 hours (instead of 1 hour).

If the patient tolerates AVB-S6-500 upon rechallenge, the premedication regimen and infusion duration should remain the same for subsequent dosing.

Infusion reactions should be managed symptomatically. Meperidine should be considered for treatment of rigors.

5.2.4 MONITORING OF DOSE ADMINISTRATION

Patients will be monitored before, during, and after the infusion with assessment of vital signs at the times specified in the Schedule of Assessment and as per **Section 5.1.3**. After the first AVB-S6-500 infusion, a 45-minute observation will be required for all patients (Cycle 0 in the AVB-S6-500 monotherapy group; Cycle 1 in the Safety Lead-In and durvalumab monotherapy groups). After the first infusion, observation will only be needed as clinically indicated.

5.3 ACCOUNTABILITY AND DISPENSATION

The investigator, or a responsible party designated by the investigator, must maintain a careful record of the inventory and disposition of the agent. The Velos IDATA System will be utilized by the MD Anderson Investigational Pharmacy services for accountability.

5.4 DISPOSITION OF UNUSED INVESTIGATIONAL STUDY DRUG

The site will account for all investigational study drug dispensed and also for appropriate destruction. Certificates of delivery and destruction must be signed.

6. TREATMENT PLAN

6.1 PROCEDURES FOR RANDOMIZATION

Subjects will be recruited from the Department of Gynecologic Oncology and Reproductive Medicine at The University of Texas MD Anderson Cancer Center. Patients with platinum resistant high grade ovarian, primary peritoneal, or fallopian tube cancers will be screened by the designated research staff and/or study investigators for eligibility. Interested patients will be approached and provided information regarding the study and potential eligibility and participation. After informed consent, screening evaluation will be performed to determine eligibility. Patients may elect to leave the study at any time.

We will enroll up to 30 evaluable subjects with platinum-resistant EOC at an expected rate of 3 subjects per month. Subjects will be evaluable for the primary objective once they have completed one cycle of combination therapy at the RP2D. Up to 12 evaluable subjects will be enrolled into the dose de-escalation combination phase (Safety Lead-in) to determine the RP2D. Once the RP2D is determined, subsequent subjects will be randomized to monotherapy arms as described below. To replace patients that are registered but do not proceed to treatment (e.g. screen failures), an additional 15 patients may be

registered; however, a maximum of 30 evaluable patients will be treated as per the protocol. Subjects will be treated until disease progression or until unacceptable toxicity. We will follow all patients for at least 12 months, and we will employ safety and efficacy monitoring rules as described in **Section 9.2.1** and **Section 9.2.2**.

Following RP2D determination, we will randomly assign patients to one of two monotherapy treatment arms (durvalumab or AVB-S6-500) at a ratio of 1 (durvalumab) to 3 (AVB-S6-500). All patients, with the exception of any who meet discontinuation criteria, will then receive combination treatment regimen.

Randomization will be carried out using CORe.

Subjects who are incorrectly enrolled but have not been initiated on treatment will be withdrawn from the study. Such subjects will be replaced. Any subjects who are incorrectly enrolled and randomized and initiated on therapy will be reported to the IRB as a protocol violation. Such subjects will be evaluated on an individual basis by the PI and the decision to continue treatment or withdraw will be based on an analysis of risk/benefit for the subject.

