2. STUDY OBJECTIVES

2.1 PRIMARY

To determine toxicity profile of the combination of AVB-S6-500 and durvalumab therapy

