6.2 DEFINITION OF DOSE-LIMITING TOXICITIES

DLTs will be evaluated during the safety lead-in (dose de-escalation phase) of the trial. The period for evaluating DLTs will be from the time of first administration of study drug until 6 weeks (1.5 cycles). Any treatment-related toxicities that first occurred during the DLT period must be followed for resolution to determine if the event qualifies as a DLT as specified in the DLT criteria below. Patients who do not remain on the study up to this time for reasons other than DLT will be replaced with another patient at the same dose level. Grading of DLTs will follow the guidelines provided in the Common Terminology Criteria for Adverse Events (CTCAE) version 5.0.

To be considered a DLT, an AE must be at least possibly related to the investigational product or regimen and meet the criteria listed below. Toxicity that is clearly and directly related to the primary disease or to another etiology is excluded from this definition. The DLT criteria are specified in the following lists.

Hematologic toxicity:

- Grade ≥ 3 neutropenia complicated by fever $>38.3^{\circ}\text{C}$
- Grade ≥ 3 neutropenia that does not improve \leq Grade 1 within 7 days
- Grade 4 neutropenia (lasting more than 7 days)
- Grade ≥ 3 thrombocytopenia with significant bleeding
- Grade 3 thrombocytopenia that is not associated with clinically significant bleeding and does not improve by at least 1 grade within 7 days
- Grade 4 thrombocytopenia (regardless of duration)
- Grade 4 anemia (regardless of duration)

Non-hematologic toxicity:

- Any Grade 4 non-immune-mediated AE
- Any Grade 4 immune-mediated AE, excluding endocrinopathies
- Any Grade 3 non-immune mediated AE, including fatigue, that does not resolve to \leq Grade 1 or baseline within 30 days with optimal medical management
- Any Grade 3 immune-mediated AE – excluding diarrhea/colitis, pneumonitis, hepatitis, rash, neurotoxicity, myocarditis, myositis/polymyositis, endocrinopathies and nephritis – that does not resolve to \leq Grade 2 or baseline within 15 days and to \leq Grade 1 within 30 days after onset of the event, despite optimal medical management including systemic corticosteroids

- Grade 3 diarrhea or colitis
- Grade 3 noninfectious pneumonitis
- Grade 2 noninfectious pneumonitis that does not resolve to \leq Grade 1 within 3 days of the initiation of maximal supportive care

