The trial will be completed after the RP2D is determined as described above. The section below is maintained in the protocol in order to reference the original design and will no longer apply.

After the RP2D is determined, subsequent patients will be randomized in a 3:1 manner for enrollment into the respective AVB-S6-500 and Durvalumab monotherapy arms. We estimate accrual rate of 3 patients per month. We anticipate a dropout rate of approximately 8-10% due to possible toxicity as seen in prior literature of checkpoint inhibitor therapy [61], [62], and subsequent inability to proceed to combination treatment. All patients who complete the monotherapy treatment phase will proceed to combination treatment, at which time receipt of at least one dose of combination therapy at the final determined dosing defines evaluable patients. As mentioned above, should the safety lead-in phase in the combination treatment require dose adjustment, only those patients who received the RP2D and completed one cycle of combination treatment will be considered evaluable for the primary outcome of response rate to combination therapy and used for making go/no-go decision as described below.

In terms of outcome assessment of response rate and toxicity to combination therapy, the Bayesian optimal phase 2 (BOP2) design is utilized to jointly monitor toxicity and efficacy [63]. The first 12 patients to receive combination treatment constitutes the first stage. Of these N=12 patients, if 1 or more responses are detected and no more than 5 DLTs are observed, the trial will proceed to the second-stage and enroll an additional 15 patients. Of note, more than 3 responses and fewer than 10 DLTs in the total study cohort will indicate statistically significant improvement in response and toxicity.

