9.1 DESCRIPTION OF ANALYSIS SETS

9.1.1 SAFETY ANALYSIS SET

Subjects who have received at least one dose of Durvalumab + AVB-S6-500 combination treatment will be included in the Safety Analysis Set. Safety will be monitored in the monotherapy phase and in the combination therapy phase.

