9.2.1 SAFETY ANALYSES

We will tabulate adverse events by grade, and relationship to study drug. We will estimate the proportion of subjects that discontinue treatment due to treatment-related adverse events with 90% confidence intervals. We will estimate the unacceptable toxicity rate with a 90% confidence interval.

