11. STUDY MANAGEMENT

11.1 MONITORING OF THE STUDY

The study will be monitored by the M.D. Anderson IND office and a protocol specific monitoring plan will be followed. We will monitor unacceptable toxicity (defined as grade 3 or greater treatment-related AEs or discontinuation of the study regimen due to side effects) independently in each monotherapy treatment arm and in subsequent combination treatment, guarding against an unacceptable toxicity rate of 40% or higher (based on published studies employing combination of other Anti-PD1/PDL1 agents), using the methods of Thall et al.[64].

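### Section 6.1 limits the primary toxicity objective to subjects who completed a combination cycle, against the any-dose safety set; separately, and minor, the DLT lists never name Grade 5

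*Combined protocol and SAP*

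**What the plan says.** **Population for the primary objective**

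- Section 2.1 gives one primary objective: "To determine toxicity profile of the combination of AVB-S6-500 and durvalumab therapy".
- Section 6.1 sets the condition for counting toward it: "Subjects will be evaluable for the primary objective once they have completed one cycle of combination therapy at the RP2D".
- Section 9.1.1 defines the safety population differently: "Subjects who have received at least one dose of Durvalumab + AVB-S6-500 combination treatment will be included in the Safety Analysis Set".
- Section 9.2.1 promises an estimate, "We will estimate the unacceptable toxicity rate with a 90% confidence interval", without saying over which subjects.
- Section 11.1 says what unacceptable toxicity is: "defined as grade 3 or greater treatment-related AEs or discontinuation of the study regimen due to side effects".
- In the Section 9 text kept only as a record of the original design, a completed cycle is required for a different endpoint: "completed one cycle of combination treatment will be considered evaluable for the primary outcome of response rate".
- Section 3.1 reports that enrollment stopped after the fifth evaluable lead-in subject.

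**DLT criteria**

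- Section 6.2 requires a DLT to meet a listed criterion. The two general entries for the most severe non-hematologic events read "Any Grade 4 non-immune-mediated AE" and "Any Grade 4 immune-mediated AE, excluding endocrinopathies".
- The general Grade 3 immune-mediated entry also leaves out endocrinopathies. No separate entry picks them up.
- A patient who leaves within the six-week window for any reason except a DLT is replaced.

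**The concern.** Whether a subject completes the first cycle depends on toxicity. A set restricted to completers therefore selects on the outcome being measured. A subject who stops in week 2 or 3 because of side effects is an event under Section 11.1 and belongs to the Section 9.1.1 set, yet Section 6.1 takes her out of both numerator and denominator. Removing an event in this way can only push the rate down. The toxicity profile is the primary objective and the treated group is very small, so the reported figure could depend visibly on which of the two rules the analyst applies, and that choice could be made after the outcomes are known.

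The DLT wording is a smaller matter. Section 8.2.1 treats Grade 5 as its own category, and the DLT lists do not mention it. Most fatal events would first meet some listed criterion. A fatal immune-mediated endocrinopathy would not, because both general immune-mediated entries exclude it. Read literally, such a death is not a DLT and the patient is replaced.

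**Working it through.** **Plan's own figure.** The documents give no expected rate of stopping in cycle 1 for toxicity and no precision for five or six subjects. The nearest figure is the 90% half-width of 0.127 for a 20% toxicity rate with 27 subjects, in the retired phase II text. It reproduces: 1.645 × √(0.20 × 0.80 / 27) = 0.127. It is not in dispute.

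**Step 1: one subject who stops in cycle 1 for side effects, no other events.** The replacement rule in Section 6.2 suggests two cases. If the event is not a DLT, the subject is replaced, so five evaluable subjects means six treated. If it is a DLT, she is not replaced, so five are treated and four complete the cycle. Exact (Clopper-Pearson) 90% intervals:

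| Case | Any-dose set (9.1.1) | Completers only (6.1) |
|---|---|---|
| Replaced | 1/6 = 17% (1% to 58%) | 0/5 = 0% (0% to 45%) |
| Not replaced | 1/5 = 20% (1% to 66%) | 0/4 = 0% (0% to 53%) |

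**Step 2: the same exclusion when k other subjects also had unacceptable toxicity.**

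- Replaced: (k+1)/6 − k/5 = 17, 13, 10, 7 and 3 points for k = 0 to 4.
- Not replaced: (k+1)/5 − k/4 = 20, 15, 10 and 5 points for k = 0 to 3.

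The 17 and 20 points are therefore maxima.

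**Step 3: expected bias.** Let p be the true rate and d the share of all subjects who stop in cycle 1 for side effects. The rate among completers is (p − d)/(1 − d), and the chance of at least one such subject among n is 1 − (1 − d)^n. The values of d are assumptions. The 9.4% in Section 1.6.2.2 is discontinuation for adverse events in durvalumab monotherapy studies with no first-cycle limit, so it is probably an upper case; 2% and 4% are assumed lower cases.

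| d | True 20% reads | True 40% reads | Chance of at least one, n = 5 to 6 |
|---|---|---|---|
| 2% | 18.4% | 38.8% | 10% to 11% |
| 4% | 16.7% | 37.5% | 18% to 22% |
| 9.4% | 11.7% | 33.8% | 39% to 45% |

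The bias is about 2 to 8 points at a true 20% and 1 to 6 points at a true 40%, the limit that Section 11.1 guards against.

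**Step 4: a fatal immune-mediated endocrinopathy against the DLT lists.**

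- The hematologic entries do not apply, and the non-immune entries do not apply by definition.
- Both general immune-mediated entries exclude it.
- The organ-specific entries cover other organs.
- The explicit endocrine exclusion covers only asymptomatic Grade 3 disorders under management, so it does not address a death either way.

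No criterion captures the event.

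**The case against.** The strongest reply on the population is that the Section 6.1 sentence concerns accrual. It sits beside the target of 30 evaluable subjects and the 3:1 randomization, it names no analysis set, and Section 9.1.1 supplies the set that Section 9.2.1 would naturally use. Section 9.2.1 also estimates discontinuation for treatment-related adverse events, which would make little sense in a set that drops early leavers. Most of this stands: the any-dose set is the likely intention, and the cycle rule looks carried over from a response-rate endpoint. But the notice in Section 9 retires only text below it. Section 6.1 comes earlier, is not marked as superseded, and ties its rule to the primary objective by name. Nothing states which rule governs.

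It is also fair that Section 2.1 names a toxicity profile, not a single rate. The unacceptable-toxicity rate is one summary of it, used here because the plan commits to estimating it.

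A reader might infer more than the documents support in four places.

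- **That one exclusion always costs 17 to 20 points.** This needs no other events. At the 2% assumption, the chance that five completers include at least one event is 1 − (1 − 0.184)^5 = 64% at a true 20% and 1 − (1 − 0.388)^5 = 91% at a true 40%.
- **That the phase II go/no-go decision is compromised.** Section 9 says that design no longer applies.
- **That leaving a non-fatal Grade 4 endocrinopathy out of the DLTs is an oversight.** Section 6.2 excludes it expressly, and Appendix A allows study drug to resume after Grade 2 to 4 endocrinopathy once the patient is stable. This is a clinical choice and is not challenged.
- **That the Grade 5 omission could still drive an unsafe escalation.** Enrollment has ended, and Section 9.2.3 requires IND Office approval before any change of dose level.

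**Conclusion.** The population conflict is real and should be fixed. Section 6.1 as written would drop from the primary toxicity objective the subjects whose treatment failed early on safety grounds. One such exclusion lowers the unacceptable-toxicity rate by at most 17 points with replacement or 20 without, and by less as other subjects have events. The expected bias is about 2 to 8 points at a true 20% and 1 to 6 points at a true 40%.

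These sizes rest on assumptions: cycle-1 toxicity dropout of 2% to 9.4%; five or six treated subjects, all at the RP2D (Section 3.1 does not state the dose); and no one else removed by the cycle rule. Subjects who leave in cycle 1 for other reasons are not modelled. The documents do not report that any subject left in cycle 1, so this is a risk in the rule and not a demonstrated error in a result. Dose finding is largely protected, because Section 6.2 keeps patients who leave for a DLT.

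The Grade 5 omission is minor and narrows to treatment-related death, with fatal immune-mediated endocrinopathy as the concrete case. With enrollment ended, it affects only the reported DLT count. Such a death is still a serious adverse event under Section 8.1.2, with a written report within 24 hours if unexpected and related, and still counts as unacceptable toxicity under Section 11.1.

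**What to change.** 1. In Section 6.1, replace the completed-cycle condition for the primary objective with a reference to the Section 9.1.1 Safety Analysis Set.
2. In Section 9.2.1, name that set as the denominator of the unacceptable-toxicity rate.
3. Keep the Section 6.2 rule for dose finding, and say in one sentence that a DLT-evaluable patient is one who completed the six-week window or had a DLT within it.
4. In Section 6.2, state that any treatment-related death in the DLT window is a DLT, whatever the organ system. Leave the exclusion of non-fatal Grade 4 endocrinopathy as it is.

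The cost is wording only, with no further patients or data. The toxicity estimate and the DLT count may look slightly less favourable.
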